## **7.0 ADVERSE EVENTS**

### **7.1 Experimental Therapy**

#### **7.1.1 One-month delayed resection**

Prostate cancer is usually a slow-growing cancer even in the setting of high-risk disease. Therefore, delaying RP doesn't impact on earlier, medium- or long-term oncologic and functional outcomes [44-46]. On a period of one month from TMA to RALP, the functional outcomes should not be affected by the TMA. In fact, the one-month delay from TMA to RP is long enough to allow for decreasing peri-prostatic edema, however short enough to avoid tissue fibrosis, retraction and adhesion that would happen with prolonged delay from TMA. The functional outcomes should be dictated/related to RALP, patients' and cancer characteristics such as nerve sparing RALP technic, urethral length, patients age, etc. The TMA will not be performed with a curative intent, in fact, it will be performed conservatively, sparing the boundaries of the prostate to avoid damage to the neurovascular bundles and the rectum. Furthermore, there will be a dose-escalation approach, where the TMA will be performed from small to larger ablation areas allowing for precise evaluation of the ablated area in each planned ablation template.

#### **7.1.2 Two-separated procedures**

The risks of the operations are according to each operation individually. Focal therapy for prostate cancer (HIFU and Cryoablation) is routinely performed by USC urologists. In fact, we have one of the largest experiences with ablation therapy for PCa in the US [42,47]. These procedures are safe with low risk of perioperative complications and lower risks of severe adverse events. In our initial series of 100 consecutive men who underwent HIFU focal therapy for PCa, approximately 13% of the patient experienced adverse events being the most common urinary retention, requiring prolonged catheterization, and urinary infection, requiring antibiotics [39]. No patient underwent additional intervention due to complications/adverse events. Additionally, there were no anesthesia-related complications. It is important to note that these patients were treated with a curative intent with large areas of ablation often extending towards to the urethra. Recent trials investigating TMA also demonstrated the feasibility and safety [26-28]. For the current PRAMA study, the TMA approach will be more conservative because the intent isn't curative, therefore the urethra and surrounding organs will be preserved. As such, we expect lower chances of side effects. The anesthesia risks related to RALP is similar to the approximately 600

---

RALPs annually performed by USC urology. The anesthesia risk shouldn't be affected by the TMA prior to RALP.

## 7.2 Adverse Event Monitoring

Adverse event data collection and reporting, which are required as part of every clinical trial, are done to ensure the safety of Subjects enrolled in the studies. Adverse events are reported in a routine manner at scheduled times during a trial. For this study, the AEs will be monitored and recorded at the day of surgery and each postop visit, per study calendar.

Additionally, certain adverse events must be reported in an expedited manner to allow for optimal monitoring of patient safety and care.

## 7.3 Definition

### 7.3.1 Definition of Adverse Event

An adverse event (AE) is any untoward medical occurrence in a patient receiving study treatment and which does not necessarily have a causal relationship with this treatment. Based on pilot data, there are no adverse events associated with performing TMA in patients who are candidates for RP. The AEs of interest for this study include:

Acute urinary retention: any episode of urinary retention following surgery, needed catheterization.

Hematuria: Any gross blood/clot in the urine, needed bladder irrigation.

### 7.3.2 Severity of Adverse Events

All adverse events will be graded according to the Clavien Dindo Classification (CDC) in the post-operative prostatectomy setting (outlined below).

The Clavien Dindo classification is available at

<https://www.ncbi.nlm.nih.gov/pmc/articles/PMC1360123/>

Adverse events are monitored and recorded in accordance with Common Terminology Criteria for Adverse Events (CTCAE) v5.0 as well, although the safety of the protocol is evaluated based on CDC.CTCAE v5.0 is available at

[https://ctep.cancer.gov/protocoldevelopment/electronic\\_applications/ctc.htm#ctc\\_50](https://ctep.cancer.gov/protocoldevelopment/electronic_applications/ctc.htm#ctc_50)

#### Clavien Dindo Classification (CDC)

Grade I	Any deviation from the normal postoperative course without the need for pharmacological treatment or surgical, endoscopic and radiological interventions Allowed therapeutic regimens are: drugs as antiemetics, antipyretics, analgetics, diuretics and electrolytes and physiotherapy. This grade also includes wound infections opened at the bedside.
Grade II	Requiring pharmacological treatment with drugs other than such allowed for grade I

---

	complications. Blood transfusions and total parenteral nutrition are also included.
Grade III	Requiring surgical, endoscopic or radiological intervention
IIIa	Intervention not under general anesthesia
IIIb	Intervention under general anesthesia
Grade IV	Life-threatening complication (including CNS complications)* requiring IC/ICU-management
IVa	Single organ dysfunction (including dialysis)
IVb	Multi organ dysfunction
Grade V	Death of a patient

### 7.3.3 Serious Adverse Events

A “serious” adverse event is defined in regulatory terminology as any untoward medical occurrence that:

1. Results in death
2. Life-threatening event
3. Requires inpatient hospitalization or prolongation of existing hospitalization
4. Results in persistent or significant disability or incapacity or substantial disruption of the ability to conduct normal life functions

### 7.3.4 Is life-threatening

Only SAEs that are judged by the Principal Investigator to be related or possibly related to TMA and not part of the expected post-operative course will be assessed and reported.

- The patient was at risk of death at the time of the event; it does not refer to an event that hypothetically might have caused death if it were more severe.

---

- Requires in-patient hospitalization or prolongation of existing hospitalization for  $\geq 24$  hours.
- Results in persistent or significant disability or incapacity.
- Is a congenital anomaly/birth defect
- Is an important medical event
- Any event that does not meet the above criteria, but that in the judgment of the investigator jeopardizes the patient, may be considered for reporting as a serious adverse event. The event may require medical or surgical intervention to prevent one of the outcomes listed in the definition of "Serious Adverse Event".

For example: allergic bronchospasm requiring intensive treatment in an emergency room or at home; convulsions that may not result in hospitalization; development of drug abuse or drug dependency.

#### **7.4 Steps to Determine If an Adverse Event Requires Expedited Reporting**

Step 1: Identify the type of adverse event using the Clavien Dindo Classification (CDC).

Step 2: Grade the adverse event using the CDC.

Step 3: Determine whether the adverse event is related to the protocol therapy  
Attribution categories are as follows:

- Definite – The AE is *clearly related* to the study treatment.
- Probable – The AE is *likely related* to the study treatment.
- Possible – The AE *may be related* to the study treatment.
- Unlikely – The AE is *unlikely related* to the study treatment.
- Unrelated – The AE is *clearly NOT related* to the study treatment.

Note: This includes all events that occur within 30 days of the last dose of protocol treatment. Any event that occurs more than 30 days after the last dose of treatment and is attributed (possibly, probably, or definitely) to the agent(s) must also be reported accordingly.

Step 4: Determine the prior experience of the adverse event.

Expected events are those that have been previously identified as resulting from administration of the agent. An adverse event is considered unexpected, for expedited reporting purposes only, when either the type of event or the severity of the event is not listed in the current known adverse events including rectal injury, urethral injury, acute urinary retention, perineal pain and uncontrollable hematuria.

#### **7.5 Reporting Requirements for Adverse Events**

- **Expedited Reporting**
  - The Principal Investigator must be notified within 24 hours of learning of any serious adverse events, that were possible related to the research procedures..

---

- The Institutional IRB will be notified in accordance with the institutional policy about any unanticipated problems involving risk to subjects or others (UPR).

The following events meet the definition of UPR:

- 1. Any serious event (injuries, side effects, deaths or other problems), which in the opinion of the Principal Investigator was unanticipated, involved risk to subjects or others, and was possibly related to the research procedures.
- 2. Any serious accidental or unintentional change to the IRB-approved protocol that alters the level of risk.
- 3. Any deviation from the protocol taken without prior IRB review to eliminate apparent immediate hazard to a research subject.
- 4. Any new information (e.g., publication, safety monitoring report, updated sponsor safety report), interim result or other finding that indicates an unexpected change to the risk/benefit ratio for the research.
- 5. Any breach in confidentiality that may involve risk to the subject or others.
- 6. Any complaint of a subject that indicates an unanticipated risk or that cannot be resolved by the Principal Investigator.
- The USC NCCC Data and Safety Monitoring Committee (DSMC) must be notified within 24 hours of submission of such reportable event to the IRB. The patient ID and the study number as well as identifier of the SAE report should be submitted to the DSMC Coordinator via email or Fax to the attention of the DSMC Coordinator at [contact].

- **Routine Reporting**
  - All other adverse events- such as those that are expected, or are unlikely or definitely not related to the study participation- are to be reported annually as part of regular data submission. For studies requiring USC DSMC review, this report should also be forwarded to the DSMC Coordinator. If USC holds the IND, a list of all toxicities will be included in the IND annual report.

## **7.6 Unblinding Procedures For Blinded and Randomized trials**

- NA

## **7.7 Monitoring Rules for Safety**

All other adverse events- such as those that are expected or are unlikely or definitely not related to the study participation- are to be reported as part of regular data submission.

---

We will pause study enrollment after 10 patients if 2 or more patients do not progress to RP and perform a thorough assessment as to ongoing safety of the study.

If a severe adverse event related to TMA occurs during TMA procedure or by follow-up phase (Day 10 ± 5) for immediate resection phase or by follow-up phase 3 (Day 40 ± 5) for delayed resection phase, we assess, discuss, and tabulate the severe adverse event.

To ensure safety, the next patient's TMA will be scheduled at least after follow-up phase of the previous patient for immediate resection phase. For delayed resection phase, the next patients for the different TMA template will be scheduled at least after follow-up phase 3 of the previous patients.

In addition, for the delayed resection phase, in the case that two in two patient who underwent the same TMA template experienced severe adverse events related to TMA, we stop to proceed the next TMA template.

We set 30% as clinically acceptable severe adverse events (defined as CDC ≥3) rate (i.e. less than 4 in 10 delayed resection cases).

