#### **4.4 Other Modalities or Procedures**

##### **4.4.1 Radical prostatectomy**

First 5 patients undergo RP immediately after TMA under the same anesthesia as their definitive treatment for PCa.

Following 10 patients undergo RP one month after TMA under the general anesthesia as their definitive treatment for PCa. This surgery is performed as standard of care.

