#### **4.5 Removal of Patients from Protocol Therapy**

Patients can be taken off the study treatment and/or study at any time at their own request, or they may be withdrawn at the discretion of the investigator for safety, behavioral or administrative reasons. The reason(s) for discontinuation of treatment will be documented and may include:

- Patient withdraws consent
- Patient is unable to comply with protocol requirements
- Patient experiences toxicity that makes continuation in the protocol unsafe
- Treating physician determines continuation on the study would not be in the patient's best interest

Notify the Principal Investigator and document the reason for study removal and the date the patient was removed from treatment in the Case Report Form. The patient should be followed-up with per protocol.

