#### **4.7 Patient Replacement**

Patients may be removed from the study at any time either via patient preference or failing to undergo either TMA or RP. If a patient is removed from the study, an additional patient may be enrolled. Patients who complete all procedures outlined in this protocol will be considered "fully evaluable", whereas those who fail to undergo any of the procedures (i.e. TMA or RP) will be considered "not fully evaluable". We will report the numbers and percent of men considered "not evaluable". If there are more than 1 or 2, we will try to figure out if there are any salient characteristics that distinguish "fully evaluable" from "not fully evaluable" patients.

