#### 5.3.8 **RP**

30 days ( $\pm$ 15days) after TMA, the robotic RP as standard of care for the prostate cancer starts under same general anesthesia. Just prior to RP, MRI/TRUS fusion transperineal biopsy will be performed under the same anesthesia of RP. Then the RP will be immediately carried out as per SOC. After RP, the patient is sent to the recovery room for monitoring. After completely recovery from the anesthesia the patient stays hospital overnight or is discharged home with the urethral Foley in place. Prescriptions are provided for: bladder antispasmodic, anti-inflammatory, and antibiotics.

---

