### **11.7.3 Data and Safety Monitoring Committee (DSMC) Oversight**

The Data and Safety Monitoring Committee (DSMC) is an independent body responsible for the safety of study subjects through the review of new protocols to ensure an adequate adverse event assessment/reporting plan, study stopping rules and through the real-time and periodic monitoring of severe adverse events (SAEs) or those AEs that

---

require expedited reporting. The DSMC performs quarterly and annual safety reviews as well as interim efficacy/futility analyses on institutional trials. DSMC procedures are detailed in USC NCCC DSM Plan available on the CISO website.

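### The section 7.7 pause for men who do not reach prostatectomy states no trigger before patient 10, is in effect about 2 of 5 delayed men, and leaves patients 11–15 unclear; checking the same count before each delayed template is a cheap improvement

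*Combined protocol and SAP*

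**What the plan says.** - **The rule.** Section 7.7: "We will pause study enrollment after 10 patients if 2 or more patients do not progress to RP". A review of whether the study remains safe follows. No earlier look is named, and nothing says whether counting goes on afterward.
- **Who can miss RP.** Section 4.4.1: "First 5 patients undergo RP immediately after TMA under the same anesthesia". The next 10 men have RP about a month after TMA. Under section 4.2 they go through the five templates in pairs: patients 6–7, 8–9, 10–11, 12–13 and 14–15.
- **When RP is due.** Section 5.3.8 sets it at 30 days, plus or minus "15days) after TMA, the robotic RP as standard of care". The section 5.5 calendar sets Day 30 ± 5. No date is given after which a man counts as not having progressed.
- **The stagger.** Section 7.7, for the delayed phase: "the next patients for the different TMA template will be scheduled at least after follow-up phase 3 of the previous patients". Section 5.4.5 describes follow-up phase 3 as a clinic visit about 10 days after RP; the calendar and section 7.7 label it Day 40 ± 5.
- **Neighboring provisions.** Section 4.5: "The reason(s) for discontinuation of treatment will be documented". Section 4.7 allows replacement ("If a patient is removed from the study, an additional patient may be enrolled") and, for men not fully evaluable, says: "If there are more than 1 or 2, we will try to figure out". Section 11.7.3: "The DSMC performs quarterly and annual safety reviews". The delayed-phase stop (two of two men on one template) and the 30% limit in section 7.7 count severe adverse events, not missed RP.

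**The concern.** The sponsor has already judged that two men who do not reach RP justify a pause and a review. The difficulty is when that judgment is applied. Half of the first ten men have almost no opportunity to miss RP, so the rule rests on about five men. It is silent while the first four delayed men are treated, and its reach over the second Template #3 man and all of delayed Templates #4 and #5 is not stated.

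Section 7.1.1 says TMA here is not curative in intent. A man who is ablated and then has no RP has not had his chosen definitive treatment within the study, although he can still have it as standard care. He also leaves the primary analysis under section 10.0. Section 4.7 lets him be replaced, and the replacement could be treated before the rule is read. The reason may simply be patient preference, which is why pausing to assess, rather than stopping, is the right response.

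**Working it through.** **Inputs.** Threshold of 2 and look after 10 patients (section 7.7); 5 immediate and 10 delayed men (section 4.4.1); delayed templates in pairs (section 4.2). The rate p of missed RP is not in the documents; 5, 10, 20 and 30% are assumptions. Misses are taken as independent at a common rate, none among patients 1–5, with outcomes known at each check. The plan states no operating characteristic for this rule, so there is no figure to reproduce.

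**Men at risk at the look.** 10 − 5 = 5 (patients 6–10), so the threshold is 2 of 5. If the phrase meant 10 delayed men, which is less likely, the look would fall at planned patient 15 of 15.

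**Chance of fewer than two misses among the first k delayed men:** S(k) = (1−p)^k + k·p·(1−p)^(k−1).

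| k | p = 5% | 10% | 20% | 30% |
|---|---|---|---|---|
| 2 | 0.9975 | 0.9900 | 0.9600 | 0.9100 |
| 4 | 0.9860 | 0.9477 | 0.8192 | 0.6517 |
| 5 | 0.9774 | 0.9185 | 0.7373 | 0.5282 |
| 6 | 0.9672 | 0.8857 | 0.6554 | 0.4202 |
| 7 | 0.9556 | 0.8503 | 0.5767 | 0.3294 |
| 8 | 0.9428 | 0.8131 | 0.5033 | 0.2553 |
| 9 | 0.9288 | 0.7748 | 0.4362 | 0.1960 |

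**Chance of a pause (5/10/20/30%).**
- Single look after patient 10, 1 − S(5): 2/8/26/47%. A 2% miss rate in the immediate men would move the 20% case only from 26.3% to 30.3%.
- Checks before each delayed template (after 2, 4, 6 and 8 delayed men), any pause while planned slots remain, 1 − S(8): 6/19/50/74%. Adding the look after patient 10 does not change this.
- The same checks, pause before patient 10, 1 − S(4): 1/5/18/35%. No such pause is stated now.
- Present rule read as continuing and checked after every man from patient 10, 1 − S(9): 7/23/56/80%. This is above the template checks because it includes a check before patient 15. If the continuing rule is checked after 5, 6 and 8 delayed men, the chance is 1 − S(8), the same as with the template checks.

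**Mean delayed men treated before a first pause or the end (10/20/30%).**
- Single look, 5 + 5·S(5): 9.59/8.69/7.64.
- Continuing, checked after 5, 6 and 8 men, 5 + S(5) + 2·S(6) + 2·S(8): 9.32/8.06/6.88.
- Continuing, checked after every man, 5 + S(5) + S(6) + S(7) + S(8) + S(9): 9.24/7.91/6.73.
- Template checks alone, 2 + 2·S(2) + 2·S(4) + 2·S(6) + 2·S(8): 9.27/7.88/6.47.
- Template checks plus the look after patient 10, 2 + 2·S(2) + S(4) + S(5) + 2·S(6) + 2·S(8): 9.24/7.79/6.35.

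With both kinds of look, the difference from a continuing rule is about 0.1/0.3/0.5 men if that rule is checked after 5, 6 and 8 men, and about 0/0.1/0.4 if it is checked after every man.

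**Why keep the patient-10 look.** If patient 10 is the second miss, template checks alone would act after patient 11, one man later than the present rule. That chance is 4p(1−p)³·p = 2.9/8.2/12.3% at 10/20/30%.

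**The case against.** The best counter-argument is the stagger. Follow-up phase 3 is described as a visit after RP. Read literally, a man without RP never has that visit, so the next template cannot be scheduled: if patients 6 and 7 both miss RP, patient 8 is held. A reader might therefore infer from the 7.7 pause alone that nothing stands between two early misses and the ablation of patients 8–10. The documents do not support so flat a statement. But the same visit is also labelled Day 40, and the stagger mentions neither a pause nor an assessment. It also does not separate men within a pair. It is a possible hold, not a dependable substitute.

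Second, nothing says the rule lapses after patient 10. It is tempting to state that patients 11–15 are uncovered, or to quote the full difference of about 11, 23 and 27 points as the gain; both need the single-look reading. If the rule continues, only earlier action is gained.

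Third, every man elected RP, so the rate may be low. Men who miss it can still have it as standard care, and this is a 15-man feasibility study sized on practical grounds. Misses caused by harm also meet the severe-adverse-event stop, reporting to the institutional review board and safety committee monitoring. All of this limits the size of the point. None of these channels pauses enrolment because RP was missed, and the absence of a stated trigger before patient 10 holds on every reading.

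**Conclusion.** The point holds as a minor-to-moderate, cheap improvement. The pause has no stated trigger before patient 10, is in effect about 2 of 5 delayed men, and is silent on patients 11–15 and on when RP counts as missed.

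The firmest gain is the chance of a pause before patient 10: about 5, 18 and 35% at assumed miss rates of 10, 20 and 30%, where none is stated now. The rise in any pause, from 8/26/47% to 19/50/74%, holds only if the present rule is one look that lapses. If it continues, the benefit is at most about half a man treated before a first pause, and close to nothing at a 10% rate.

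A reader might take the differences in men treated as men spared for good. They are not: the rule is a pause, and enrolment may resume. All sizes rest on assumed rates, independence, no misses in patients 1–5 and outcomes known at each check. That last assumption favors the single look, since nothing makes patient 11 wait for patient 10.

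**What to change.** In section 7.7:

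- Count every man, in either phase, who had TMA and has not had RP by the end of the protocol window. Day 45 (30 + 15, from section 5.3.8) would serve once that section and the calendar agree. Include men who are later replaced.
- Check the count before each new delayed template, at the existing stagger, once every earlier man has had RP or passed the window.
- Keep the look after patient 10, before patient 11 is treated. Check also before any replacement or extension patient.
- Pause enrolment and carry out the assessment already planned as soon as the count reaches two.

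The threshold and the response do not change, and no men are added. The cost is a few sentences plus some modest downsides:

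- A review pause becomes somewhat more likely when the true rate is low: about 6% against 2% for a single look at a 5% rate, and 19% against 8% at 10%.
- An RP postponed past the window for scheduling reasons would count until the assessment explains it.
- A template start could wait a few more days for Day 45.
- The look before patient 11 works as calculated only if patient 10's RP status is known by then, which may mean one wait inside the Template #3 pair. Otherwise it rests on patients 6–9, as the check before Template #3 does.

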## 10.7 Data Analyses Plans

All patients who sign the consent form will be registered and entered the database. For each patient, we will list whether he received the assigned protocol (and if not, the reasons), the outcome of the procedures, compliance with the protocol (and reasons for failure to comply), adverse events with any of the procedures, MRI results, and targeted biopsy results.

- The data from the immediate resection phase and delayed resection phase will be separately evaluated. The observed ablated area in immediate resected prostatectomy specimen based on TTC staining will be compared with the predicted ablation area according to the template. The tissue viability will be evaluated by HE staining on delayed resection prostatectomy specimen.
- The comparison of the difference between the treatment effect dimensions measured histologically on the prostatectomy specimen resected after TMA and the predictive ablation charts provided by the manufacturer will be performed. For this analysis, the data from immediate resection phase and delayed resection phase are separately evaluated.
- The comparison between the treatment effect dimensions measured histologically on the prostatectomy specimen resected one month after TMA, compared to post TMA dimensions measured on the pre-RP mpMRI.
- To evaluate the intra/post-operative safety of TMA, we defined 30% as clinically acceptable severe adverse events (defined as CDC  $\geq 3$ ) rate. If the severe adverse events occur less than 30% (equivalent to less than 4 cases in 10 cases) for the delayed ablation phase, the feasibility of TMA is proved.

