### Delayed resection phase

If a severe adverse event related to TMA occurs during TMA procedure or by follow-up phase 3 (Day  $40 \pm 5$ ), we assess, discuss, and tabulate the severe adverse event. In the case that two in two patient who underwent the same TMA template experienced severe adverse events related to TMA, we stop to proceed the next TMA template. For this evaluation, TMA-related adverse events include rectal injury, urethral injury, acute urinary retention, and uncontrollable hematuria.

Adverse events are also recorded in accordance with Common Terminology Criteria for Adverse Events (CTCAE) v5.0.

- TMA procedure duration: probe-in / probe-out time, ablation time will be recorded.
- The ablation location in the prostate as seen in the KOELIS 3D map and the ablation location observed histologically on the prostatectomy specimen will be recorded.

---

- The change in functional outcomes between baseline and each follow-up visit, using IPSS, IIEF-5, EPIC-26 and uroflowmetry is recorded. For delayed resection phase, functional outcomes between baseline and follow-up phase 2 will be estimated as average change.
- The post-TMA MRI and prostate biopsy performed just prior to the delayed radical prostatectomy will be reported.

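### Delayed phase: the 4-in-10 severe-event limit triggers no interim action, so Template 5 can start after the phase can no longer pass (rare; optional change)

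*Combined protocol and SAP*

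**What the plan says.** Section 4.2 assigns two men to each of five templates in the delayed phase (patients 6 to 15). Template 5 is the overlapping double 7.5-minute ablation.

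Section 7.7 sets these controls on escalation:

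- **Wait between templates:** "the next patients for the different TMA template will be scheduled at least after follow-up phase 3 of the previous patients".
- **Stopping rule:** escalation ends "in the case that two in two patient who underwent the same TMA template experienced severe adverse events related to TMA". Section 10.7 repeats the rule, with the action "we stop to proceed the next TMA template".
- **Overall limit:** a 30% rate of severe events (CDC grade 3 or higher), glossed as "less than 4 in 10 delayed resection cases".
- **Cumulative pause:** "We will pause study enrollment after 10 patients if 2 or more patients do not progress to RP". This counts men who miss prostatectomy, not severe events.
- **Case review:** every TMA-related severe event up to follow-up phase 3 is reviewed and tabulated, with no threshold attached.

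Section 10.7 makes the limit the final verdict: "If the severe adverse events occur less than 30% (equivalent to less than 4 cases in 10 cases) for the delayed ablation phase", then "the feasibility of TMA is proved". No section ties the limit to an action before the end of the phase.

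**The concern.** The stopping rule looks at one pair of men at a time, while the verdict looks at all ten. Events spread evenly over the templates never trigger the first but can defeat the second. Two men could then be given the largest ablation when the phase has already exceeded the limit the plan calls clinically acceptable, and no number in the protocol obliges anyone to pause.

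The limit is also ambiguous. Section 10.7 treats below 30% and below 4 in 10 as equivalent, and they differ at exactly 3 events. A trigger cannot be set until that is settled.

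A smaller matter of wording concerns Template 5. There is no next template to withhold after it, so if both men there had a severe TMA-related event and nobody else did, the phase would still be declared feasible at 2 of 10.

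**Working it through.** **Inputs.** From the plan: five templates of two men (4.2); stop if both men on a template have a TMA-related severe event (7.7, 10.7); failing count 4 (7.7), or 3 under the strict percentage wording (10.7). The plan gives no CDC grade 3+ rate for TMA, so the rate per man, p, is assumed at 5, 10, 20 and 30%, constant and independent between men.

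**The plan's own figure.** 3/10 = 30% and 4/10 = 40%. Fewer than 4 in 10 therefore matches at most 30%, with failing count 4. Strictly below 30% already fails at 3, so the two wordings are not equivalent.

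**Reaching 4 before Template 5.** Without a 2-of-2 stop each template contributes at most one event. The count is at most 3 after Template 3, and it is 4 after Template 4 only by the path 1-1-1-1. That is 4/8 = 50% so far. The final count must be 4 to 6 of 10, so the phase fails whatever happens on Template 5.

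Write a = 2p(1−p) for exactly one event on a template and b = (1−p)² for none.

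- Failing count 4: P(Template 5 starts at 4) = a⁴.
- Failing count 3: either Templates 1 to 3 give 1-1-1, so that Template 4 starts at 3, or one of the first three has no event and the other two and Template 4 have one each, so that Template 5 starts at 3. P = a³ + 3ba³ = a³(1+3b).
- Template 5 wording case, 0-0-0-0-2: P = (1−p)⁸p².

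| p | a | b | a⁴ | a³(1+3b) | (1−p)⁸p² |
|---|---|---|---|---|---|
| 5% | 0.095 | 0.9025 | 0.00008 | 0.003 | 0.0017 |
| 10% | 0.18 | 0.81 | 0.0010 | 0.020 | 0.0043 |
| 20% | 0.32 | 0.64 | 0.0105 | 0.096 | 0.0067 |
| 30% | 0.42 | 0.49 | 0.0311 | 0.183 | 0.0052 |

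Example at p = 20%: 0.32⁴ = 0.0105; 0.32³ × (1 + 3 × 0.64) = 0.03277 × 2.92 = 0.096.

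**Rising risk.** With assumed rates rising over the five templates as 5, 5, 10, 15, 20%, the 1-1-1-1 path has probability 0.095 × 0.095 × 0.18 × 0.255 = 0.0004. With 10, 15, 20, 25, 30% it is 0.18 × 0.255 × 0.32 × 0.375 = 0.0055. The Template 5 wording case is 0.019 in both.

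**What the choice of wording does to the verdict.** If all ten men are treated, the chance of passing with at most 3 events, against at most 2, is 0.987 against 0.930 at p = 10%, 0.879 against 0.678 at 20%, and 0.650 against 0.383 at 30%.

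**The case against.** **The rates may be low.** CDC grade III means an intervention was needed. The nearest data, 100 focal HIFU patients in Section 7.1.2, showed about 13% with any adverse event and no additional intervention. Zero in 100 has a one-sided 95% upper bound of 1 − 0.05^(1/100), about 3%. At 3% the main path has probability (2 × 0.03 × 0.97)⁴ = 0.00001, about 1 in 87,000. HIFU is only a proxy, but this stands as a reason for low priority.

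**Oversight exists.** A reader might infer that Template 5 would go ahead unexamined. The documents do not support that. Section 7.7 requires each TMA-related severe event to be reviewed and tabulated, so a fourth event would be considered beside the earlier three. Section 11.7.3 gives the DSMC ongoing monitoring and quarterly reviews. Four templates at Day 40 ± 5 each take at least 140 to 180 days, so a quarterly review should fall before Template 5. Section 4.2 allows the physician to modify delivery, Section 7.5 sends unexpected changes in risk to the IRB, and each template is first tried once in the immediate phase. What survives is narrower: none of these carries a count. Section 7.4 also lists the main TMA complications as known events, so some may go to routine annual reporting under 7.5; since severity can make an event unexpected, that routing is possible, not certain.

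**All-cause counting.** The 30% sentence does not mention relatedness, so a reader might infer that prostatectomy complications count too and that the gap is larger. With an assumed 5 or 10% unrelated risk per man, a further template starts at 4 or more in 0.4 to 12.8% of trials over the same TMA rates. These figures deserve little weight. Section 10.7 introduces the criterion as an evaluation of TMA safety and then lists the TMA-related events for the delayed phase, Section 7.3.4 limits the SAEs assessed and reported to those at least possibly related to TMA, and the unrelated rates appear nowhere in the documents. The criterion should still say what it counts.

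**Template 5.** The verdict is a statement about the phase, and no claim for each template is planned. Reading it as endorsing Template 5 goes beyond the text, so this is a wording preference, not an error.

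**Conclusion.** The point holds, at optional severity. The only numeric stopping rule on severe events in the delayed phase is 2-of-2 within a template, and the overall limit has no interim action. Under the count of 4, Template 5 can start after the phase can no longer pass, in 0.008 to 3.1% of trials at assumed TMA-related rates of 5 to 30%. The inconsistency at 3 of 10 matters more in practice: if 3 is the failing count, a further template, from Template 4 on, starts at or above it in 0.3 to 18.3% of trials. All of these figures rest on assumed, independent and constant rates; the rising-rate cases leave the main path below 1%. The documents do not support a finding that safety oversight is absent. They support a finding that it lacks a number.

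**What to change.** 1. **Section 7.7:** at the existing follow-up phase 3 wait before each new template, check the cumulative number of delayed-phase men with a TMA-related CDC grade 3+ event, and pause for DSMC review once it reaches the failing count. This is a pause for review, not an automatic stop.
2. **Sections 7.7 and 10.7:** state the limit one way, for example at most 30%, that is, fewer than 4 of 10, with failing count 4. Say that it counts TMA-related events, as the 2-of-2 rule does.
3. **Section 10.7, optional wording:** the feasibility statement does not extend to a template that met 2-of-2, including Template 5. This leaves the phase verdict and the lower templates unchanged.

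The cost is a few sentences by amendment, with no added visits, patients or routine waiting. The downside is an occasional pause, as often as the main path occurs: 0.008, 0.1, 1.0 and 3.1% of trials at 5, 10, 20 and 30% with failing count 4, or 0.3, 2.0, 9.6 and 18.3% if the sponsor means 3.
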